### Evaluation of cognitive function:

 Difference in reaction time and working memory in patients receiving Plenadren and conventional Cortisone at baseline and 6-12 months after treatment initiation, specifically targeting reaction time and working memory. Cognitive test administration using Memoro, a web-based cognitive test platform developed by [name] and [name], NTNU (28-30).

### Evaluation of safety:

- Differences in occurrence of adverse events, registered during the study
  - Adverse events
  - Serious adverse events
  - o Register any adrenal crisis symptoms or treatment (separate form)

© 2015-2021 TransCelerate BioPharma

Doc. No. CT 2.01.01. Valid from 31 Jan 2022. Only the electronic version is valid.

Page 18 of 65

Objectives	Endpoints
Primary	
Differences in health-related quality of life (HRQoL) scores in patients receiving Plenadren and conventional Cortisone at time of diagnosis and 1, 6, and 12 months	HRQoL score
Secondary	
Differences in clinical markers of cardiometabolic health in patients receiving Plenadren and conventional thrice daily Cortisone at time of diagnosis and 6 and 12 months after treatment initiation.	
 
Blood pressure: systolic blood pressure and diastolic blood pressure
 
Body weight, waist circumference, and body mass index
 
Levels of total cholesterol, low-density lipoprotein (LDL) cholesterol, high-density lipoprotein (HDL) cholesterol, triglycerides
 
Levels of glucose, insulin, and HOMA index
 

Differences in hair cortisol concentrations time of diagnosis and in patients receiving Plenadren and conventional Cortisone at 6 and 12 months after treatment initiation.	Hair cortisol level
Differences in salivary cortisol day curves in patients receiving Plenadren and conventional Cortisone at 6 and 12 months after treatment initiation.	Salivary cortisol day curves
Differences in the urinary cortisol metabolome in patients receiving Pleandren and conventional Cortisone at 6 and 12 months after treatment initiation.	24 h urine cortisol and metabolites
Differences in sleep quality in patients receiving Plenadren and conventional Cortisone at 6-12 months after treatment initiation, using the following instruments:	
 
Sleep diary (https://helse-bergen.no/nasjonal-kompetansetjeneste-for-sovnsykdommer-sovno/sovndagbok-sovno)
 
Actigraphy
 
Sleep radar (Somnofy)
 

© 2015-2021 TransCelerate BioPharma

Doc. No. CT 2.01.01. Valid from 31 Jan 2022.

Only the electronic version is valid.

Page 19 of 65

	Objectives		Endpoints
reco	ferences in cognitive function in patients eiving Plenadren and conventional rtisone at 1, 6 and 12 months after atment initiation:	•	Reaction time, working memory and verbal learning and memory Cognitive test administration using Memoro, a web-based cognitive test platform developed by [name] and [name], NTNU. Biomarker for brain plasticity (BDNF)
con	ferences in bone metabolism and body imposition receiving Plenadren and aventional Cortisone at 1, 6 and 12 months or treatment initiation:	•	Bone mineral density (BMD) and Body composition Bone markers
	ferences in occurence of adverse events, istrated during the study	•	Adverse events Serious adverse events
	ferences in occurence of adverse events, istered during the study	•	Adverse events Serious adverse events Register any adrenal crisis symptoms or treatment (separate form)

© 2015-2021 TransCelerate BioPharma

[figure not shown]
Doc. No. CT 2.01.01. Valid from 31 Jan 2022.

Only the electronic version is valid.

Page 20 of 65

# 4. Study Design

# 4.1. Overall Design

This is a phase 4 RRCT designed to test if oral replacement treatment with Plenadren is superior to conventional oral treatment with Cortisone in participants with newly diagnosed PAI between 16-80 years of age. The participants are assigned to one of two treatment types in parallel for the duration of the study. The primary outcome is improvement of HRQoL. To avoid the potential bias we will only include newly diagnosed patients as these will be treatment-naïve and unable to compare with other forms of replacement therapy.

The end of the study is defined as the date of the last visit of the last participant in the study.

A participant is considered to have completed the study if the participant has completed all periods of the study including the last visit.

# 4.2. Scientific Rationale for Study Design

### 4.2.1. Choice of study design

The standard glucocorticoid replacement therapy has been largely unchanged since the 1950s, in Norway consisting of cortisone. An extended-release formulation of hydrocortisone marketed under the name Plenadren was approved for replacement therapy in 2011 and is currently used by about 20 percent of patients with PAI in Norway (3). Being an orphan drug, approval was based on an open study documenting reduction of weight, blood pressure, and glucose levels (17), and more recently, a beneficial effect on the urinary cortisol metabolome (18). Follow-up studies have confirmed that long-term use of Plenadren is safe, but superiority to conventional

© 2015-2021 TransCelerate BioPharma

Doc. No. CT 2.01.01. Valid from 31 Jan 2022.

Only the electronic version is valid.

Page 21 of 65

Cortisone has not been proven (19). Another factor is that a daily dose of Plenadren (NOK 130) costs almost 30 times that of Cortisone (NOK 4).

Despite the high-ranked position in the hierarchy of clinical evidence, double-blind RCTs have limitations that need to be acknowledged, including prohibitive costs of adequately powered studies and strict inclusion criteria that limit the real-life applicability (19). In the setting of glucocorticoid replacement in PAI, a RCT is further hindered by the lack of a placebo medication for Plenadren, which is not available. Furthermore, the pharmaceutical industry has shown no interest to perform a double-blinded RCT trial that could challenge the current notion that Plenadren provides a better and more physiological replacement of glucocorticoids.

PAI is a rare, and clinical trials in recently diagnosed glucocorticoid-naïve patients non-existent but are needed to avoid the bias of previous patient treatment experience. Furthermore, long term national studies are required to achieve sufficient participant number. Recently, RRCTs have emerged as a new clinical trial paradigm to test treatment options, maintaining the advantages of traditional RCTs, but at a much lower cost and closer to real-life practice (19).

### 4.2.2. Patient Input into Design

Patient representative [name] has been part of the study group from the planning stage and have given valuable input into the protocol and consent form, e.g. clarifying the text and making it more understandable. The patient organization have a particular interest in studies of fatigue in PAI, and fatigue, a component of HRQoL is a main focus of the study. They are also very focused on diversity and availability of drugs for replacement therapy and the current study aligns well with the Morbus Addison Association of Norway's goals.

The patient representative have read and provided input to the protocol and the consent form, mainly to clarify the text and make it more understandable

# 4.3. Justification for glucocorticoid dose

In patients randomized to conventional Cortisone, the initial replacement dosage will be 25 mg per day according to current clinical routine. Patients randomized to Plenadren will receive an initial dosage of 20 mg, as in previous clinical trials (17). One week after inclusion and treatment initiation, the patient will return for blood tests for evaluation and individual adjustment of the dosage. No study-specific dose increase or dose reduction protocols apply. Participant dosage is titrated by the participants' endocrinologist if needed using a structured symptom history (Pearce's questions form). Cortisol measurement at 1 and 4 hours after morning dose is measured to detect gross overdosing or lack of absorption of drug. Saliva cortisol is sampled at 1 and 4 hours after morning dose at 6 and 12 months.

© 2015-2021 TransCelerate BioPharma

Doc. No. CT 2.01.01. Valid from 31 Jan 2022.

Only the electronic version is valid.

Page 22 of 65

# 5. Study Population

Potentially eligible study participants are all newly diagnosed patients in Norway with PAI independent of etiology. The diagnostic criteria are basal serum cortisol < 100 nmol/L combined with p-ACTH > 2 x upper reference limit; or co-syntropin stimulated serum cortisol < 485 nmol/L and p-ACTH > 2 x upper reference limit (29).

Prospective approval of protocol deviations to recruitment and enrollment criteria, also known as protocol waivers or exemptions, is not permitted.

### 5.1. Inclusion Criteria

Participants are eligible to be included in the study only if all of the following criteria apply:

- 1. Age between 16-80 years.
- 2. Established PAI according to the diagnostic criteria as specified above.
- 3. Participants must be recently diagnosed, specifically treated with glucocorticoid replacement therapy for less than 31 days prior to inclusion to secure treatment naivety.
- 4. Women of childbearing potential (WOCBP)\* must have a negative pregnancy test performed at the time of screening.
- 5. Participants must be capable of giving signed informed consent as described in Appendix 1 which includes compliance with the requirements and restrictions listed in the informed consent form (ICF) and in this protocol.

### 5.2. Exclusion Criteria

Participants are excluded from the study if any of the following criteria apply:

© 2015-2021 TransCelerate BioPharma

Doc. No. CT 2.01.01. Valid from 31 Jan 2022. Only the electronic version is valid.

Page 23 of 65

\* For the purpose of this study, a woman is considered of childbearing potential (WOCBP), i.e. fertile, following menarche and until becoming post-menopausal unless permanently sterile. Permanent sterilisation methods include hysterectomy, bilateral salpingectomy and bilateral oophorectomy. A postmenopausal state is defined as no menses for 12 months without an alternative medical cause. A high follicle stimulating hormone (FSH) level in the postmenopausal range may be used to confirm a post-menopausal state in women not using hormonal contraception or hormonal replacement therapy. However in the absence of 12 months of amenorrhea, a single FSH measurement is insufficient.

### **Medical conditions**

- 1. Ongoing treatment for active malignant disease
- 2. Severe hepatic or renal disease
- 3. Sever psychiatric disease
- 4. Chronic abuse of alcohol or drug abuse
- 5. Current pregnancy, and if the participant plan to become pregnant during the 12 months of study participation.
- 6. Known hypersensitivity to the active substance or any of the excipients.

### **Prior/Concomitant Therapy**

7. High dose glucocorticoid therapy for other disease during last three months prior to screening. This includes steroid injections for allergic disease and injections into joints. Local glucocorticoid treatment (inhalations, nasal spray or creams for use on skin) is allowed.

### **Prior/Concurrent Clinical Study Experience**

8. Participation in another blinded clinical study involving an investigational medicinal product within 1 month prior to study inclusion

### **Diagnostic Assessments**

9. Participants not fulfilling the diagnostic criteria for PAI, as specified above in 5.1.

### **Other Exclusion Criteria**

10. Not applicable

# 5.3. Lifestyle Considerations

There are no lifestyle restrictions for study inclusion.

### **5.3.1.** Other Restrictions

There are no other restrictions for study inclusion.

### 5.4. Screen Failures

A screen failure occurs when a participant who has consented to participate in the clinical study is not subsequently assigned to study intervention and entered in the study. A minimal set of screen failure information is required to ensure transparent reporting of screen failure participants to meet the CONSORT publishing requirements and to respond to queries from regulatory authorities. Minimal information includes demography, screen failure details, eligibility criteria, and any SAE.

© 2015-2021 TransCelerate BioPharma

Doc. No. CT 2.01.01. Valid from 31 Jan 2022. Only the electronic version is valid.

Page 24 of 65

# 6. Study Intervention(s) and Concomitant Therapy

# 6.1. Study Intervention(s) Administered

Participants will be randomized to replacement therapy with either Cortisone or Plenadren for the duration of the study. Starting dose for Cortisone is thrice daily (12.5 mg morning, and 6.25 mg at noon and 6.25 mg in the afternoon). Starting dose for Plenadren is once daily 20 mg (morning). Both investigational drugs have marketing authorization and will be prescribed by the patients treating endocrinologist as for patients not included in the study. Thus, there are no study specific drug labelling or packaging.

Since all participants are newly diagnosed with PAI, treatment with fludrocortisone is also required from time of diagnosis as per standard care. Concomitant fludrocortisone treatment will not be a subject of any study specific restrictions.

Table 6.1. Study Intervention(s) Administered

Intervention Label	Cortison	Plenadren
Intervention Name	Cortison	Plenadren
Intervention Description	Oral, TID	Oral, OD
Туре	Cortisone acetate	Hydrocortisone
Dose Formulation	Tablet	Tablet
Unit Dose Strength(s)	25mg	20mg
Dosage Level(s)	12.5mg +6.25mg+6.25mg	20mg OD
Route of Administration	Oral	Oral
Use	Active comparator	Test
IMP and NIMP/AxMP.	IMP	IMP
Sourcing	Provided by the pharmacy per prescription as per standard care	Provided by the pharmacy per prescription as per standard care
Packaging and Labeling	Not applicable	Not applicable

Table 6.2. Study Arm(s)

Arm Title	Cortison	Plenadren
Arm Type	Active comparator	Test

© 2015-2021 TransCelerate BioPharma

Doc. No. CT 2.01.01. Valid from 31 Jan 2022.

Only the electronic version is valid.

Page 25 of 65

# 6.2. Preparation, Handling, Storage, and Accountability

Both Plenadren and Cortison are provided by the pharmacy per prescription as standard care. The medication is stored and handled according to the pharmacy's procedure. There will be no drug inventory accountability since the drug is taken form the pharmacy's storage.

### **6.3.** Assignment to Study Intervention

This study will be using randomization, performed in blocks of four and performed at the central study site at HUH. The study investigators will contact HUH by calling a dedicated phone number. A study nurse will assign treatment type.

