### Objectives, Endpoints, and Estimands:

© 2015-2021 TransCelerate BioPharma

Doc. No. CT 2.01.01. Valid from 31 Jan 2022. Only the electronic version is valid.

Page 8 of 65

**Overall design:** Registry-based, open-label, single center, randomized, controlled academic investigational medicine study.

**Brief Summary:** The purpose of this study is to compare quality of life, metabolic parameter, bone health and sleep quality with Plenadren or Cortisone in patients with primary adrenal insufficiency.

**Treatment duration**: 12 months

Visit number and frequency: 6 visits

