### 1.2. Schema

Potentially eligible study participants are all newly diagnosed patients with primary adrenal insufficiency (PAI). The diagnostic criteria are basal serum cortisol < 100 nmol/L combined with p-ACTH > 2 x upper reference limit: or synacthen—stimulated serum cortisol < 485 and p-ACTH > 2 x upper reference limit.

In patients randomized to conventional Cortisone, the initial replacement dosage will be 25 mg divided in three doses according to current clinical routine. Patients randomized to Plenadren will receive an initial dosage of 20 mg, as in previous clinical trials (17). One week after inclusion and treatment initiation, the patient will return for blood tests for evaluation and individual adjustment of the dosage.

The Section of Endocrinology at The Department of Medicine at Haukeland University Hospital (HUH) and The Endocrine Medicine Group at Department of Clinical Science at the University of Bergen (UiB) have built up a unit for translational research in endocrinology. The outpatient clinic is staffed with experienced personnel in handling patients and samples. The Fasttrack infrastructure to be used for registration of study information, is well established and used for all outpatient contacts at Section of endocrinology, Department of Medicine, Haukeland University Hospital. The system is available at all hospitals in Norway through Noklus Diabetes and can be used by the network of dedicated physicians. It has recently been used in clinical studies (27), and proven to be a safe, robust and efficient way to register study information. An array of autoantibody assays are available, including 21-hydroxylase autoantibodies. The core facility for

© 2015-2021 TransCelerate BioPharma

Doc. No. CT 2.01.01. Valid from 31 Jan 2022. Only the electronic version is valid.

Page 9 of 65

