### 6.4. Blinding, Masking

This is an open-label study; potential bias will be reduced by central randomization.

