### 8.1.2. Randomization and Baseline visit (Visit 2)

Randomization to either Cortisone or Plenadren can be done after screening and attaining an informed consent, either before or at visit 2 (day 0). The including investigator will the study nurse at HUH on a dedicated phone number and the consenting participant will be randomized to either treatment type. Randomization will be performed centrally and in blocks of four to secure equal assignment number in each group. A prescription for the study drug including recommended dosage will thereafter be provided to the patient.

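### A single printed block size of four, allocated by a nurse at a hospital that also appears to recruit, would let anyone who sees all earlier allocations work out 16 of 50

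*Protocol*

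**What the plan says.** Protocol section 6.3 states that randomization is "performed in blocks of four and performed at the central study site at HUH". The procedure is by telephone: "The study investigators will contact HUH by calling a dedicated phone number", after which "A study nurse will assign treatment type". Section 8.1.2 repeats the block size and gives the reason: "Randomization will be performed centrally and in blocks of four to secure equal assignment number in each group". Neither section mentions varying block sizes, stratification, or keeping the list and past allocations from those who enrol.

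Section 6.4 reads: "This is an open-label study; potential bias will be reduced by central randomization". It names no other measure. Sections 2.1 and 4.1 add that only treatment-naïve patients are enrolled. That deals with comparison against earlier therapy, not with predictable allocation.

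Section 6.3 calls HUH the central study site. Of the endocrine clinic there, section 1.2 says: "The outpatient clinic is staffed with experienced personnel in handling patients and samples". The synopsis describes the trial as: "Registry-based, open-label, single center, randomized, controlled academic investigational medicine study". Sections 5 and 10.1.4, however, describe recruitment throughout Norway. The synopsis plans 50 randomized participants, and section 3 makes patient-reported quality of life the primary endpoint.

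**The concern.** Central randomization guards against selection bias only if the person deciding whether and when to enrol cannot foresee the next arm. Three features weaken this. The block size is fixed and printed in the document that investigators work from. Treatment is open, so past allocations are known to those who treat the patients. The list is operated at a hospital that also runs a clinic for this disease. Anyone who can follow the sequence within a block can tell when one arm is used up.

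If a recruiter could foresee the arm, the decision to approach a patient, or the day on which to telephone, could depend on it. In an open-label trial of about 50 patients with a subjective primary endpoint, that would create differences between the groups at entry which a longitudinal model cannot be relied on to remove.

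**Working it through.** The protocol gives no figure for predictability, so there is none to reproduce.

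**Inputs**
- Block size 4 (sections 6.3 and 8.1.2).
- Equal assignment, so 2 + 2 in each block (section 8.1.2).
- N = 50 (synopsis).
- Assumption: one unstratified list, since no stratification is described.

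**1. Observer who sees every allocation: certain deductions.** There are six equally likely orders of a 2 + 2 block.
- Positions 1 and 2 are never determined.
- Position 3 is determined if the first two were the same arm, probability 2/6 = 1/3.
- Position 4 is always determined.
- Per block: 1/3 + 1 = 4/3, and (4/3)/4 = 33.3%.
- Fifty patients make 12 complete blocks plus 2. The 2 extra add nothing, so 12 × 4/3 = 16, and 16/50 = 32%.

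**2. Same observer, guessing the less-filled arm.**
- Position 1: 1/2.
- Position 2: 2/3.
- Position 3: 1/3 × 1 + 2/3 × 1/2 = 2/3.
- Position 4: 1.
- Per block: 1/2 + 2/3 + 2/3 + 1 = 17/6, and (17/6)/4 = 70.8%.
- For 50 patients: 12 × 17/6 + 1/2 + 2/3 = 35.2, or 70.3%, against 50% by chance.

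**3. Observer who sees only a share p of allocations.** As an upper bound, suppose that this person knows every block position. An own patient is certain only if two earlier seen patients in the block had the same arm.
- Position 3: p²/3.
- Position 4: p³ (all three earlier patients seen) + 3p²(1 − p) × 1/3 (exactly two seen, same arm) = p².
- Average over four positions: (p²/3 + p²)/4 = p²/3.

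| Share seen | Certain among own patients, at most |
|---|---|
| 100% | 33.3% |
| 75% | 18.8% |
| 50% | 8.3% |
| 25% | 2.1% |
| 10% | 0.3% |

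**4. Randomly varying block sizes.** Here 3,000 lists of 50 were simulated for each design. The observer sees every allocation, knows which sizes are possible, and updates by Bayes' rule.

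| Block sizes | Certain | Best guess correct |
|---|---|---|
| 4 only | 32.0% | 70.3% |
| 4 and 6 | 5.6% | 69.0% |
| 4, 6 and 8 | 2.2% | 67.7% |

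Varying the sizes removes most certain deductions and little of the guessing advantage.

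**The case against.** The strongest objection is that the decisive step is inferred. No sentence says that those who enrol at HUH see the list or earlier allocations, or even states outright that HUH recruits. The protocol says only that a nurse answers a dedicated line. Arrangements for holding the list may also be set in operational documents that are not shown. This stands: 32% is the figure for a fully informed observer. It does not show what any named group knows.

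A reader might infer that every investigator can deduce a third of allocations. The documents do not support that. Recruitment is described as national with telephone allocation, and a physician who sees only local patients could deduce far less (step 3). The high figure would apply to all recruiters only if the trial really is single center, as the synopsis says and sections 5 and 10.1.4 contradict.

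Other provisions limit steering:
- Randomization follows screening and consent (section 8.1.2).
- Glucocorticoid treatment before inclusion must be shorter than 31 days (section 5.1), so a patient cannot be held back indefinitely.
- All newly diagnosed patients in the stated age range are to be asked (section 10.1.4).
- A screening log records everyone screened and the reasons for failure (section 8).
- Eligibility waivers are not permitted (section 5).

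These narrow the risk without closing it. Whether and when to approach a patient precedes the log. The call to HUH can be timed after consent within a screening window of up to 31 days (section 1.3).

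**Conclusion.** The point holds in conditional form, as a minor design improvement. A person involved in enrolment who sees all earlier allocations could deduce 16 of 50 (32%) with certainty and guess about 70% correctly. For someone who sees a quarter of them, the certain share is at most about 2%. The figures rest on one unstratified list in complete 2 + 2 blocks, 50 patients, and an observer who knows where each block starts. That HUH staff are such observers is plausible from the wording on the central site, the clinic and the single center, but it is not stated.

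A reader might go further and infer that allocations will be steered or that the result is compromised. Predictability shows an opening for selection bias. It does not show that bias occurs, and nothing in the protocol allows its effect on the quality-of-life difference to be calculated.

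**What to change.** For the remaining allocations:

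1. Have the list generated and held by someone with no part in recruitment, and keep the running allocations from recruiters. This is the essential step, because varying the blocks leaves guessing at about 68–69%.
2. Use randomly varying block sizes, for example 4, 6 and 8. Certain deductions then fall to about 2% (about 6% with 4 and 6 only), even if the possible sizes are known.
3. Remove the block size from sections 6.3 and 8.1.2 and put it in a restricted randomization document. Say in section 6.3 who holds the list and that this person does not recruit.
4. Reconcile the single-center description in the synopsis with the national recruitment in sections 5 and 10.1.4, since it decides how many recruiters could follow the sequence.

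The cost is one new list, a short protocol change and an arrangement for independent holding of the list. Visits, sample size and treatment are unchanged. Final arm sizes may differ by up to about four patients (half of an unfinished block of eight), against at most two with blocks of four. A switch in the middle of a block could add up to two more.
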